4.12.5. Per Protocol Population

The per protocol population is defined as all patients who have received at least 1 dose of MIRV, excluding patients with protocol deviations in the following categories: Patients -

- whose tumors do not have FR α positivity as defined by the Ventana FOLR1 Assay and/or
- patients without a documented platinum allergy who had only 1 prior line of platinum, and/or
- who do not meet the eligibility criterion of being platinum sensitive, and/or
- other critical/major protocol deviations that deemed affecting primary and/or key secondary objectives. The final list of critical/major protocol deviations leading to the removal of patients from the per protocol population will be finalized and signed off before the database lock for the final ORR analysis.

4.12.6. ADA-Evaluable Population

The ADA-Evaluable population includes all patients in the safety population who had baseline and at least one valid post baseline ADA result.

4.13. Data Display Characteristics

Data displays produced for this study will include summary tables, data listings, and figures.

Data listings will report the data reported in the clinical database or derived for each patient. Data will be ordered by patient number, and date/time of assessment if applicable. When expedient, additional levels of ordering hierarchy may reflect subsets of assessments within patients. Data listings will not display patient initials.

Summary tables will display summary statistics calculated for the analysis population, unless described otherwise.

The summary statistics displayed will be a function of the type of data associated with the summarized assessment. Unless stated otherwise, continuous data will be summarized with the number of non-missing values, mean, standard deviation, minimum, median, and maximum. Categorical data will be summarized with the number of non-missing values and the numbers of values equal to each of the possible values. Percentages of patients with each of the possible values will be calculated from the number of patients in the corresponding analysis population, unless stated otherwise. Some continuous variables may also be grouped into categorical levels and evaluated in frequency tables.

5. PATIENT ACCOUNTABILITY

5.1. Patient Characteristics

Patient characteristics will be summarized and listed for the Safety population. These summaries will also be produced for the Efficacy Evaluable population if more than 5% of patients in the Safety population are excluded from the Efficacy Evaluable population.

5.1.1. Demography

Data collected about the following patient characteristics at the screening visit will be summarized as follows:

- Age is collected in the clinical database at the time of patient registration. As this is a global study, there are certain regions where local regulations prohibit the collection of a complete date of birth. Therefore, age will not be recalculated for analysis purposes. The collected age will be used for summarization.
- Sex
 - Childbearing potential (female only, yes/no)
- Ethnicity
- Race
- Region
- Country

All demographic data, including informed consent date, will be listed.

5.1.2. Baseline Height, Weight, and AIBW

Baseline height, weight, BSA, and AIBW will be summarized and presented in a listing.

5.1.3. Medical History

Medical history will be coded using Medical Dictionary for Regulatory Affairs (MedDRA) (Version 24.0 or later) and graded using Common Terminology Criteria for Adverse Events (CTCAE) version 5.0, associating lower-level terms with preferred terms (PTs) and system organ classes (SOCs) by the primary hierarchy. Medical histories will be summarized as the number and percentage of patients who reported at least 1 medical history event and number and percentage of patients who reported at least 1 medical history event in each SOC. Within each SOC, tables will display the number and percentage of patients reporting at least 1 medical history event as designated by PT. All medical history information will be listed.

5.1.4. Disease Characteristics, Prior Therapy, and Gene Mutations

A summary of the following elements will be provided:

- ECOG performance status (0/1).
- Primary diagnosis (epithelial ovarian cancer, fallopian tube cancer, primary peritoneal cancer, other).
- Histology.
- Disease stage at initial diagnosis.
- Histologic grade.
- Prior radiotherapy (yes/no).
- Prior systemic therapy.
 - The number of prior systemic therapies is defined as the number of distinct treatment regimens.
 - Number of lines of prior platinum.
- Prior cancer related surgery (yes/no).
- Prior exposure to doxorubicin (yes/no), taxanes (yes/no).
- Prior exposure to PARP inhibitors (yes/no/uncertain).
 - If patient participated in a double-blind randomized trial comparing PARP inhibitor to placebo and the actual treatment was unknown, patient will be summarized under 'uncertain' category.
- Any *BRCA* mutations (BRCA1 or BRCA2 positive, *BRCA1*, *BRCA2*, no/unkown).
- Primary platinum-free interval (months, ≤ 12 months vs > 12 months).
Defined as time from last dose of 1st line platinum therapy to the date of disease progression and/or relapse following 1st line therapy.
- Most recent Platinum-free interval (months, ≤ 12 months vs > 12 months).

Defined as time from last dose of the latest line platinum therapy to the date of disease progression and/or relapse following that line of therapy.

- Prior non-platinum line of therapy (yes/no)

Listings of all collected data related to disease characteristics and prior therapy will be provided.

5.2. Patient Disposition

5.2.1. Screened and Treated Patients

The number and percentage of patients who were screened, treated (Safety population), not treated (screen failure), and reason for screen failure will be summarized overall, and by geographic region (North America and Europe), country, and site.

5.2.2. Patient Disposition

A summary of patient disposition will summarize, for the Safety population, the number of patients treated and the reason for treatment and study discontinuation. Percentage of patients who withdrew for each reason on the End-of-Treatment and End-of-Study forms will be calculated using all members of the relevant population for the denominator.

The number and percentage of Safety population included in each analysis population will be presented.

5.2.3. Protocol Deviations and Population Inclusions

Protocol deviations will be captured in a protocol deviation log. A listing of patients with any protocol deviation will be provided for the Safety population.

6. EFFICACY ANALYSES

The main efficacy analyses will use data from the Efficacy Evaluable population based on Investigator's assessment. Sensitivity analyses will be performed with BICR assessment.

6.1. Efficacy Outcomes

6.1.1. Best Overall Response

Best overall response (BOR) for a patient is the best response designation as assessed by the Investigator recorded between the date of first dose of MIRV and the date of objectively documented PD per RECIST Version 1.1, the date of the start of new anti-cancer therapy, or the date of study discontinuation, whichever occurs first. When an analysis cutoff date is implemented, only radiological assessments occurring on or prior to the cutoff date will be used for analysis. Patients with an overall response of CR or PR must have a repeat tumor assessment performed no less than 4 weeks (28 days) after the criteria for response are first met. When stable disease is the best overall response, it must meet the minimum duration of 35 days (6 weeks – 1 week window = 35 days from the date of first dose of MIRV). The confirmatory scan is valid following treatment discontinuation if the patient has not started a new anti-cancer therapy. Once

a patient has a confirmed response, tumor response may only be recorded as continued response or progressive disease.

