Progressive Disease (PD)	At least a 20% increase in the SoD of target lesion, taken as reference the smallest (nadir) SoD since and including baseline. In addition to the relative increase of 20%, the SoD must also demonstrate an absolute increase of at least 5 mm.
Stable Disease (SD)	Neither sufficient shrinkage to qualify for PR nor sufficient increase to qualify for PD.
Not Applicable (N/A)	No target lesions identified at baseline
Unable to Evaluate (UE)	One or more target lesions are not imaged and the remainder of the SoD compared with the nadir SoD does not meet the criteria for PD
If the target lesion for a patient meets the criteria for both PR and PD at a given time point, the target lesion response is PD.	
If the nadir SoD is 0 (ie, the patient had a prior target lesion CR), the re-appearance of any prior target lesions to any degree constitutes PD.	
Non-Target Lesion TPR	
Complete Response (CR)	Disappearance of all non-target lesions and normalization of tumor marker level if tumor marker at baseline is above the upper limit of normal (ULN). All lymph nodes must be non-pathological in size (< 10 mm short axis).
Non-CR/Non-PD	Persistence of one or more non-target lesion(s) and/or maintenance of CA-125 above the normal limits if CA-125 at baseline is above the ULN.
Progressive Disease (PD)	Unequivocal progression of non-target lesions. Unequivocal progression should not normally trump target lesion status. It must be representative of overall disease status change, not a single lesion increase.
Not Applicable (N/A)	No non-target lesions identified at baseline.
Unable to Evaluate (UE)	One or more non-target lesions are not imaged and the remaining non-target lesions do not meet the criteria for PD.

If the target lesion for a patient meets the criteria for both PR and PD at a given time point, the target lesion response is PD.

If the nadir SoD is 0 (ie, the patient had a prior target lesion CR), the re-appearance of any prior target lesions to any degree constitutes PD.

New Lesion TPR

Yes	Lesion present at follow-up visit either for the very first time or re-appearing (ie, lesion was present at baseline, disappeared at a follow-up visit and re-appeared later).
No	No new lesions present at follow-up
Unable to Evaluate (UE)	Patient non assessed or incompletely assessed for new lesion

Determining Overall TPR

Target Lesion TPR	Non-Target TPR	New Lesions TPR	Overall TPR
CR	CR or NA	No	CR*
CR	Non-CR/non-PD	No	PR*
CR	UE	No	PR*

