PR	Non-PD or NA or UE	No	PR*
SD	Non-PD or NA or UE	No	SD
UE	Non-PD	No	UE
PD	Any	No or Yes or UE	PD
Any	PD	No or Yes or UE	PD
Any	Any	Yes	PD
NA	CR	No	CR*
NA	Non-CR/non-PD	No	Non-CR/non-PD
Non-PD	Non-PD	UE	UE

Any = CR, PR, SD, PD, NA, or UE; CR = complete response; NA = not applicable (no such lesions at Screening); PD = progressive disease; PR = partial response; SD = stable disease; TPR = time point response; UE = unable to evaluate.

The overall response at a given time point does not depend upon the overall response assigned at any prior time point.

*Patients with an overall response of CR or PR must have a repeat tumor assessment performed no less than 4 weeks after the criteria for response are first met.

Confirmation - The main goal of confirmation of objective response is to avoid overestimating the observed response rate. For patients with an overall response of PR or CR a given time point, changes in tumor measurements must be confirmed by repeat assessments that should be performed no less than 4 weeks after the criteria for response are first met. However, the presence or absence of confirmation is not considered when assigning a time point response.

Best Overall Response - Best overall response, incorporating confirmation requirements, will be derived during statistical analysis from the series of time point responses and need not be considered when assigning response at any time point.

Document ID: CLIN-00067	Title: IMGN853-0419 Clinical Study Protocol	Version: 2.0
Legacy ID: 26587		Approved Date: 12/22/202

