3.2.2. Power and Sample Size

The primary endpoint of this study is ORR as assessed by the Investigator. The study is designed to test the null hypothesis that the ORR is $\leq 28\%$ using an optimal Simon's two-stage design ([Simon 1989](#)) without a planned pause in enrollment given preliminary efficacy and established safety of MIRV.

The optimal two-stage design to test the null hypothesis that the ORR is $\leq 28\%$ versus the alternative that the ORR is $\geq 48\%$ has an expected sample size of 37.74 and a probability of early termination of 0.762. If the ORR is $\leq 28\%$, there is a 0.024 probability of rejecting the null hypothesis (the target 1-sided alpha value was 0.025). If the ORR is $\geq 48\%$, there is a 0.9

probability of rejecting the null hypothesis. After testing the drug on 28 efficacy evaluable patients in the first stage, the study will be terminated for futility if 9 or fewer respond. If the study goes on to the second stage, a total of 69 efficacy evaluable patients will be enrolled. If the total number responding is more than 26, the null hypothesis is rejected.

Approximately 75 patients will be enrolled so that a total of 69 patients will be efficacy evaluable.

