6.1.1.2. DOR

DOR is defined as the time from the date of the first response (CR or PR), whichever occurs first, to the date of PD or death from any cause, whichever occurs first. DOR is only defined for patients who have a confirmed BOR of CR or PR.

Per the BOR definition, patients with an overall response of CR or PR must have a repeat tumor assessment performed no less than 4 weeks after the criteria for response are first met. The first date at which a CR or PR response was noted will be used to calculate DOR, not the date of the confirmatory tumor assessment.

Patients who started a new anti-cancer therapy prior to documented PD or death will be censored at the last radiological assessment prior to initiation of new anti-cancer therapy. Patients who did not have PD or death or new anti-cancer therapy will be censored at the date of their last radiological assessment. Patients who had PD or death after missing 2 or more consecutive radiological assessments (PD or death date - last radiological assessment date +1 \geq 105 days or \geq 231 days if the assessment schedule has changed from every 6 weeks [+1 week] to every 12 weeks [+3 weeks] after Week 36 or after discontinuing from study treatment per local requirements). will be censored at the date of their last radiological assessment before the missing radiological assessment.

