6.1.2. PFS

PFS is defined as the time from the date of first dose of MIRV until the date of PD or death from any cause, whichever occurs first. PFS is defined based on radiological assessments and determined by the Investigator. Clinical progression is not considered a progression endpoint.

[Table 3](#) summarizes the rules to be used for PFS. When an analysis cutoff date is implemented, only data (deaths and radiological assessments) occurring on or prior to the cutoff date will be used for analysis.

Table 3: PFS Definitions

Situation	Date of PFS Event or Censoring	Outcome
No post-baseline radiological assessments, and patient did not die within 105 days of first dose	Date of first dose	Censored
No post-baseline radiological assessments, and patient died within 105 days of first dose	Date of death	Death
Death	Date of death	Death
Radiological Progression	Date of first radiological assessment indicating progression .	Progression
New anti-cancer therapy prior to PD or death (including palliative radiotherapy during study treatment)	Date of last radiological assessment prior to the start of the new anticancer therapy	Censored
No death or PD	Date of last radiological assessment	Censored
PD or death after missing 2 or more consecutive radiological assessments (PD or death date - last radiological assessment date +1 \geq 105 days or \geq 231 days if the assessment schedule has changed from every 6 weeks [+1 week] to every 12 weeks [+3 weeks] after Week 36 or after discontinuing from study treatment per local requirements).	Date of last adequate radiological assessment showing no PD	Censored

6.1.3. OS

OS is defined as the time from the date of first dose until the date of death from any cause.

Patients who are alive or lost to follow-up at the analysis are censored at the last known date at which they were known to be alive.

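### BOR, DOR and PFS do not share one definition of new anti-cancer therapy or of an assessable scan, so irradiated responses could enter the primary ORR and unevaluable scans can set censoring dates

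*SAP*

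**What the plan says.** **New anti-cancer therapy.** In SAP 6.1.1 the BOR window closes at PD, at the start of new anti-cancer therapy or at study discontinuation. A confirmatory scan after stopping treatment counts only if no such therapy has begun. SAP 6.1.1.2 censors DOR at the last scan before such therapy. None of these rules mentions radiotherapy. The matching row of PFS Table 3 (SAP 6.1.2) does: "New anti-cancer therapy prior to PD or death (including palliative radiotherapy during study treatment".

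**Status after confirmation.** SAP 6.1.1 says that once "a patient has a confirmed response, tumor response may only be recorded as continued response or progressive disease". Protocol Appendix B has a UE category, which for target lesions applies when "One or more target lesions are not imaged" and what remains does not meet PD. It also states: "The overall response at a given time point does not depend upon the overall response assigned at any prior time point".

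**Which scan counts.** For responders without an event, SAP 6.1.1.2 says: "Patients who did not have PD or death or new anti-cancer therapy will be censored at the date of their last radiological assessment". The Table 3 rows for no event and for new therapy also use the last radiological assessment without qualification. Both endpoints measure the missed-scan gap (105 or 231 days) from that assessment. Only the censoring date in the Table 3 missed-scan row is qualified: "Date of last adequate radiological assessment showing no PD". The SAP does not define adequate.

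**The concern.** ORR is the primary endpoint and DOR the key secondary, and both are read from the same scans as PFS.

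- **Radiotherapy.** A programmer could code the BOR and DOR rules with or without it. Without it, a target lesion that shrinks after irradiation can produce a confirmed PR credited to the study drug. In the same patient PFS would be censored before the radiotherapy while DOR ran on.
- **Unevaluable scans.** The two-label rule and Appendix B cannot both be followed when a responder's scan is incomplete and shows no PD. Taken literally, the only label left is continued response. Whatever the label, the DOR rule lets that scan set the censoring date, so follow-up is credited from imaging that could not be assessed.

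SAP section 9, which lists departures from the protocol, names only the number of assessments required before the primary analysis. The BICR analysis (SAP 6.5) uses the same methods, so it does not resolve either point.

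**Working it through.** **1. Reproduce the design (SAP 3.2.2).** Inputs: n1 = 28, stop at 9 or fewer responses; n = 69, reject above 26; p0 = 0.28, p1 = 0.48. With X1 ~ Bin(28, p) and X2 ~ Bin(41, p):

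P(reject) = sum over x1 = 10 to 28 of P(X1 = x1) × P(X2 ≥ 27 − x1)

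- At p = 0.28: 0.0245. The SAP says "there is a 0.024 probability of rejecting the null hypothesis (the target 1-sided alpha value was 0.025".
- At p = 0.48: 0.9001 (stated 0.9).
- Probability of early termination: 0.7624 (stated 0.762).
- Expected N: 28 + (1 − 0.7624) × 41 = 37.74 (as stated).

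**2. Irradiated responses and ORR.** Each adds 1/69 = 1.45 points. The documents give no radiotherapy frequency, so assume an average of k such responses per 69 on top of a true 28%, that is p = 0.28 + k/69. The last column is the single-stage chance of 28 or more responses out of 69, because 28 is the smallest count whose Clopper-Pearson lower bound exceeds 28%, as SAP 4.10 requires (27/69 gives 27.6%, 28/69 gives 28.9%).

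| k (assumed) | p | Simon rule, 27 or more | SAP 4.10 rule, 28 or more |
|---|---|---|---|
| 0 | 0.2800 | 0.0245 | 0.0164 |
| 1 | 0.2945 | 0.0445 | 0.0315 |
| 2 | 0.3090 | 0.0752 | 0.0561 |
| 3 | 0.3235 | 0.1186 | 0.0929 |

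**3. Two constructed patients.**

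- SD at Week 6, radiotherapy to a target lesion at Week 8, PR at Week 12, confirmed at Week 18. Bare term read narrowly: confirmed responder. Table 3 definition: the BOR window closes at Week 8 and BOR is SD (42 days, above the 35-day minimum).
- PR at Week 6, confirmed at Week 12, radiotherapy at Week 14, PD at Week 30. Narrow reading: DOR event after 24 weeks (168 days). Table 3 definition: DOR censored after 6 weeks (42 days). PFS is censored at Week 12 on either reading of the BOR and DOR rules.

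**4. Unevaluable scans and an individual DOR.** At nominal spacing, an unevaluable last scan in a responder without an event moves censoring 6 × 7 = 42 days later, or 12 × 7 = 84 days after Week 36.

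Now take two unevaluable scans followed by PD. Measured from the last evaluable scan, the gap is 3 × 42 + 1 = 127 days (at least 105), or 3 × 84 + 1 = 253 days (at least 231), so the PD would be censored. Measured from the last scan of any kind, it is 43 or 85 days and the PD stays an event. Keeping an event works against a long DOR, so the two effects pull in opposite directions.

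**5. Net effect on Kaplan-Meier DOR.** Simulation with assumed inputs: 20,000 responders, exponential DOR with median 8 months, protocol scan schedule, data cut-off 8 to 26 months after first dose. Results are 18-month restricted mean DOR in months.

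| Share of scans unevaluable (assumed) | Any scan counts | Only evaluable scans count |
|---|---|---|
| 5% | 9.96 | 9.99 |
| 10% | 10.02 | 10.08 |
| 20% | 10.16 | 10.31 |
| 30% | 10.38 | 10.61 |

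For radiotherapy, with no unevaluable scans and 25% of responders irradiated before progression (assumed), the means without and with censoring at radiotherapy are:

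- PD hazard ratio after radiotherapy 0.25: 10.51 and 9.87.
- Hazard ratio 1: 9.80 and 9.75.
- Hazard ratio 4: 8.98 and 9.81.

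**The case against.** **Radiotherapy is read from silence.** BOR, the confirmatory scan and DOR all stop at new anti-cancer therapy, and the Table 3 parenthesis can be read as explaining that term everywhere. The protocol synopsis lists palliative radiotherapy among prohibited non-study anticancer agents. SAP 4.3 gives one imputation rule for the start of subsequent therapy and names both PFS and BOR, which suggests a shared variable. On-study radiotherapy would also be a protocol deviation. This stands to the extent that a reader might infer that radiotherapy is excluded as a cut-off for BOR and DOR, and no passage says so. It does not remove the ambiguity. The parenthesis would be needless if the bare term covered radiotherapy, SAP 6.6 lists only drug classes plus an other category, and Protocol 5.8.4 does not name radiotherapy.

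**The direction of bias is not shown.** A reader might infer that these rules lengthen DOR and that both gaps favour the drug. Steps 4 and 5 do not support that: counting unevaluable scans gave an equal or slightly shorter mean DOR, and the radiotherapy effect went either way. This objection stands in full.

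**DOR is not generally looser than PFS.** The 105- and 231-day limits and most rows match. The unqualified last scan is a weakness of both endpoints. This also stands.

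**The two-label sentence cannot move ORR.** It applies only after confirmation, and DOR ends only at PD or death, so the label by itself moves no event date. This is correct: only the radiotherapy point reaches the primary endpoint, and restoring UE without changing the censoring scan would leave DOR as it is.

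**Conclusion.** The inconsistency is real and should be corrected.

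- **Primary endpoint.** The exposure is an ambiguity, not a stated rule. If the narrow reading is programmed, each irradiated responder adds 1.45 points to ORR. An assumed average of one to three per 69 takes the chance of passing the Simon rule at a true 28% from 0.0245 to between 0.0445 and 0.1186. The actual number could be zero.
- **DOR.** An unevaluable last scan moves an individual censoring date 42 or 84 days later at nominal spacing. The net effect on the Kaplan-Meier curve is roughly neutral under the simulated assumptions, and its direction is not established. The case for change is that the stated rule credits follow-up from scans that could not be assessed, and that the same patient can have conflicting DOR and PFS histories.
- **Consistency with the protocol.** The two-label rule conflicts with the UE category and the independent time-point responses in Appendix B, and SAP section 9 does not declare it.

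The gap between the 27-responder rule in SAP 3.2.2 and the 28 implied by SAP 4.10 is a separate matter. It bears here only in that one or two responders can decide the result.

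**What to change.** 1. Define new anti-cancer therapy once in the SAP, with the Table 3 content including on-study palliative radiotherapy, and apply it to BOR, the confirmatory-scan rule, ORR, DOR and PFS.
2. Amend SAP 6.1.1 so that UE may be recorded after a confirmed response, in line with Appendix B.
3. Define an adequate assessment as one whose overall time-point response is not UE. Use the last adequate assessment for every DOR and PFS censoring date and every missed-scan gap, including the no-event and new-therapy rows.
4. Carry the same definitions into the BICR analyses.

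The cost is SAP wording and programming; no new data are needed. DOR may change a little in either direction (in the simulation, evaluable-only scans raised the restricted mean by 0.03 to 0.23 months), and a counted responder may be lost. SAP 2.1 allows changes before final database lock. After that, the rule actually applied should be documented in the study report as a deviation from the SAP, with the number of responders and DOR times it affects.
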